**Evobrutinib**

**Phase IIb in Rheumatoid Arthritis  
MS200527-0060**

---

Every effort should be made to collect CCI [REDACTED] according to the Schedule of Assessments at the exact nominal time relative to dosing. Samples will not be considered protocol deviations as long as the actual collection date and time is recorded and is within the window referenced in the Schedule of Assessments.

For subjects randomized to placebo treatment, CCI [REDACTED] samples will be collected but not analyzed unless determined necessary by the Investigator and/or Sponsor. CCI [REDACTED]

Samples will be collected, labeled, processed, stored, and shipped as detailed in the laboratory manual.

CCI [REDACTED]

**Evobrutinib**

**Phase IIb in Rheumatoid Arthritis**  
**MS200527-0060**

---

CCI

CCI

## 7.7 Assessment of Symptoms and Health Related Quality of Life (HRQoL)

### 7.7.1 Medical Outcomes Study 36-item Short-Form Health Survey

The SF-36v2 is a 36-item scale constructed to survey HRQoL on eight domains: limitations in physical activities due to health problems; limitations in social activities due to physical or emotional problems; limitations in usual role activities due to physical health problems; bodily pain; general mental health (psychological distress and well-being); limitations in usual role activities due to emotional problems; vitality (energy and fatigue); and general health perceptions (Ware 1992).

The SF-36v2 has a 4 weeks recall period and yields scale scores for each of the eight health domains, and 2 summary measures of physical and mental health: the Physical Component Summary and Mental Component Summary.

### 7.7.2 Functional Assessment of Chronic Illness Therapy-Fatigue

The Functional Assessment of Chronic Illness Therapy (FACIT)-Fatigue is a 13-item questionnaire that assesses self-reported fatigue and its impact upon daily activities and function

(Wolfe 1996). It uses a 5-point Likert-type scale (0 = not at all; 1 = a little bit; 2 = somewhat; 3 = quite a bit; 4 = very much). As each of the 13 items of the FACIT-Fatigue scale ranges from 0–4, the range of possible scores is 0–52, with 0 being the worst possible score and 52 the best. To obtain the 0–52 score, each negatively worded item response is recoded so that 0 is a bad response and 4 is good response. All responses are added with equal weight to obtain the total score.

CCI

[REDACTED]

[REDACTED]

[REDACTED]

[REDACTED]

## 7.8 Other Assessments

CCI

[REDACTED]

[REDACTED]

## 8 Statistics

### 8.1 Sample Size

The primary endpoint of the trial is the ACR20 response at Week 12.

A sample size of 80 evaluable subjects per group will provide approximately 90% power at an  $\alpha$  of 0.05, 2-sided significance level to detect a difference in Week 12 ACR20 response proportion between evobrutinib- and placebo-treated subjects, assuming a placebo response proportion of 30% to 45% and an expected treatment benefit of 30%, after adjusting for multiple comparisons

## Evobrutinib

### Phase IIb in Rheumatoid Arthritis MS200527-0060

---

of 3 dose comparisons with placebo. For the same range of placebo response rate, the sample size of 80 evaluable subjects per group will also provide adequate power (approximately 80%) for the expected difference of 25%.

To account for reduced information provided by the Modified Intent-to-Treat (mITT) analysis set, due to subject dropout and protocol noncompliance, occurring at a rate of approximately 11% over a 12-week period, approximately 90 subjects per group will be enrolled. The sample size was calculated using a chi-squared test of the odds ratio in nQuery Advisor® 7.0.

The Japanese cohort size was determined to provide an evaluation of consistency in the Week 12 ACR20 response proportion between the non-Japan and Japan regions. Assuming that:

- (i) the Week 12 ACR20 response proportion in the placebo group is 0.30 for both the non-Japan and Japan regions,
- (ii) the Week 12 ACR20 response proportion due to each of the 3 evobrutinib dose groups is 0.60 for both regions, so that the true underlying effect size is 0.30 for both regions,
- (iii) a total evaluable sample size of 320 (ie, 240:80 randomization for evobrutinib:placebo) is involved in analysis of the two regions,

and applying “Method 2” from the Pharmaceuticals and Medical Devices Agency Guidance, 32 evaluable subjects in the Japanese cohort are required so that both observed region-specific effect sizes exceed 0.10 with probability of approximately 80%. Taking into account a loss of information due to 10% dropout at Week 12, the total number of Japanese subjects to be randomized is 36, or 10% of the total planned enrollment of 360 subjects. The sample size was calculated via simulations with SAS version 9.3. The power is the average of 3 estimated probabilities, with each estimate based on 10,000 simulations.

For the evaluation of MRI data, assuming a minimum effect size of 0.7 for the difference in the change from Baseline in the OMERACT RAMRIS individual scores for osteitis or synovitis at Week 12 between at least one dose and placebo, at a 2-sided  $\alpha = 0.05$ , a sample size of 40 evaluable subjects per group with MRI data will provide approximately 80% power using the Wilcoxon rank-sum test in nQuery Advisor® 7.0. The same sample size will provide approximately 70% power for an effect size of 0.6. To account for approximately 11% dropout and nonevaluable MRI data, approximately 45 subjects per arm will be enrolled in the MRI study. Since there were no high-quality data available to form the basis for accurate sample size calculations for RAMRIS scores involving a study population similar to that planned for the present study, the assumed effect size of 0.7 is considered comparable to those reported in the published studies (Conaghan 2011, Genovese 2016a, Genovese 2016b).

## 8.2 Randomization

A randomized allocation schedule for IMP assignment will be generated by a third party vendor who is not on the study team. Randomization will occur using the IWRS.

## Evobrutinib

### Phase IIb in Rheumatoid Arthritis MS200527-0060

---

Eligible subjects will be randomized into 1 of 3 evobrutinib arms (25 mg once daily, 75 mg once daily, or 50 mg twice daily) or the placebo arm in a ratio of 1:1:1:1 stratified by whether or not they are in the MRI substudy (Yes, No) and by region (US, Western Europe, Japan, and the rest of world), so that within each treatment arm, there will be approximately 90 subjects, with approximately 45 subjects included in the MRI substudy to ensure approximately 80 evaluable subjects per arm for the primary analysis, and approximately 40 evaluable subjects per arm for the MRI analysis.

To ensure an adequate number of evaluable MRI subjects in the MRI substudy, recruitment of non-MRI subjects into the study may be capped. If a subject's baseline MRI indicates lack of osteitis and synovitis, additional subjects may be added to the MRI stratum to account for these subjects. Should the MRI substudy recruitment prove more difficult than anticipated, the Sponsor reserves the right to terminate the MRI substudy. Should this be done, all sites would be allowed to recruit non-MRI subjects into the study.

### 8.3 Endpoints

#### 8.3.1 Primary Endpoint

The primary efficacy endpoint is ACR20 response assessed using hsCRP (ACR20) at Week 12.

#### 8.3.2 Secondary Endpoints

The key secondary efficacy endpoints are:

- DAS28-hsCRP low disease activity (DAS28 < 3.2) rate at Week 12
- DAS28-hsCRP remission (DAS28 < 2.6) rate at Week 12
- ACR 50% (ACR50) response assessed using hsCRP at Week 12
- ACR 70% (ACR70) response assessed using hsCRP at Week 12.

The key secondary safety endpoints are:

- The nature, severity, and occurrence of AEs and serious AEs (SAEs)
- Absolute values and change from Baseline in:
  - Vital signs
  - ECG parameters including RR interval, PR interval, QRS duration, QT interval, and QTcF interval
  - Serum Ig levels (IgG, IgA, IgM)
  - Total B cell counts
  - Clinical laboratory parameters.

## Evobrutinib

### Phase IIb in Rheumatoid Arthritis MS200527-0060

---

Other secondary efficacy endpoints are:

At Week 12:

- Achieving American College of Rheumatology/European League Against Rheumatism (EULAR) Boolean remission
- Achieving Clinical Disease Activity Index (CDAI) score  $\leq 2.8$  (CDAI remission)
- Achieving Simplified Disease Activity Index (SDAI) score  $\leq 3.3$  (SDAI remission)
- EULAR Responder Index (based on DAS-hsCRP)
- ACR hybrid scores computed using hsCRP
- Change from Baseline in DAS28-hsCRP
- Change from Baseline in CDAI and SDAI
- Changes and percentage changes from Baseline of individual components of the ACR Core Set
- Imaging:
  - Change from Baseline in Outcome Measures in Rheumatology Clinical Trials (OMERACT) Rheumatoid Arthritis Magnetic Resonance Imaging Scoring System (RAMRIS) scores (designated hand, minimal assessed joints: wrist, metacarpophalangeal (MCP) joints #1 to #5) for subjects in the MRI substudy:
    - Synovitis score
    - Bone marrow edema (osteitis) score.
- Changes from Baseline of Physical Function:
  - Health Assessment Questionnaire – Disability Index (HAQ-DI).
- Changes from Baseline of HRQoL:
  - Medical Outcomes Study 36-item Short Form Health Survey (SF-36)
  - Functional Assessment of Chronic Illness Therapy (FACIT)-Fatigue.

A large, stylized logo consisting of the letters 'C', 'C', and 'I' in a bold, red, sans-serif font. The letters are set against a solid black rectangular background. The 'C's are slightly overlapping, and the 'I' is a simple vertical bar.

**Evobrutinib**

**Phase IIb in Rheumatoid Arthritis  
MS200527-0060**

---

CCI

CCI

## 8.4 Analysis Sets

For the purposes of analysis, the following analysis sets are defined in the following table:

Population	Description
Enrolled	All participants who sign informed consent
Intent-to-treat (ITT)	The ITT analysis set will include all subjects randomly allocated to a treatment, based on the intention to treat “as randomized” principle (ie, the planned treatment regimen rather than the actual treatment given in case of any difference).
Modified intent-to-treat (mITT)	The mITT analysis set will include all randomized subjects who received at least one dose of IMP (evobrutinib or placebo). Subjects in the mITT analysis set will be included in the treatment group as randomized.
Per-Protocol (PP)	The PP analysis set will include all randomized and treated subjects who do not have any clinically important protocol deviations.
MRI	The MRI analysis set will include all randomized subjects who have at least 1 post dose MRI assessment.
Safety (SAF)	The SAF analysis set will include all subjects who receive at least 1 dose of IMP (evobrutinib or placebo). Subjects will be analyzed according to the actual treatment they receive.

CCI

The mITT analysis set will be used for the purpose of efficacy analysis unless otherwise stated; the SAF analysis set will be used for the purpose of safety analysis; and the PP analysis set will be used for the purpose of sensitivity analysis of the primary efficacy endpoint.

### 8.4.1 Subgroups

The following subgroups may be considered for primary/key secondary efficacy analyses:

- Region: US, Western Europe, Japan, the rest of world
- MRI substudy participation: Yes/No
- Ethnicity: Japanese/Non-Japanese
- Gender: Male/Female.

Other subgroups may be defined in the SAP.

## **8.5 Description of Statistical Analyses**

### **8.5.1 General Considerations**

A general description of the statistical methods to be used to analyze the efficacy and safety data is outlined below. Prior to locking of the database for the study, a detailed SAP will be finalized.

Any changes to the data analysis methods described in the protocol will require an amendment only if a principal feature of the protocol is affected. Any other changes to the planned data analysis that does not require a protocol amendment will be described in the SAP and the CTR. Additional exploratory analyses will be conducted as deemed appropriate.

A 2-sided  $\alpha$  level of 0.05 will be applied for tests of treatment effect within the study.

For the purpose of statistical analyses, baseline is defined as the last assessment prior to first dose.

In general, continuous variables will be summarized descriptively using the number of observations (N), mean, standard deviation (SD), median, first quartile (Q1), third quartile (Q3), minimum, and maximum. Categorical variables will be summarized using frequency counts and percentages.

Statistical analysis will be performed using the computer program package SAS® System for Windows (version 9.4 or higher; SAS Institute, Cary North Carolina, USA).

#### **Missing Data Handling:**

For the primary and key secondary endpoints of ACR response, the Last Observation Carried Forward will be used as the primary method for the imputation of missing values of the ACR components. For the ACR20 response at Week 12, a subject will be considered as a nonresponder if the subject discontinues prior to Week 12. Other imputation methods will be provided in the SAP as additional sensitivity analyses of the primary endpoint.

Missing data for all other secondary efficacy endpoints of binary data will be handled using a similar manner to ACR20. Further details for each endpoint will be provided in the SAP.

For the MRI analysis, a Missing At Random (MAR) pattern will be assumed for missing data in the Mixed Model for Repeated Measures.

Details of handling missing data for all other secondary efficacy endpoints of continuous data will be provided in the SAP.

### **Multiplicity Adjustment:**

A family-wise Type I error rate (FWER) at the primary analysis will be controlled at the 2-sided 0.05 significance level for the 3 pairwise comparisons of evobrutinib dose versus placebo, using the Hochberg procedure. Further details will be provided in the SAP.

## **8.5.2 Analysis of Primary Endpoint**

### **8.5.2.1 Efficacy Endpoints**

The primary analysis of ACR20 at Week 12 will be based on the mITT analysis set using Last Observation Carried Forward for imputation of missing values of each ACR component. A subject will be considered as a nonresponder if the subject discontinues prior to Week 12.

The estimate of the odds ratio (OR), together with the associated 2-sided 95% CI and p-value, comparing each evobrutinib dose group to placebo, will be provided based on a logistic regression model for the odds of ACR20 response, with evobrutinib dose group or placebo as a factor and adjustment for covariates based on randomization strata (region, MRI-substudy participation). In order to further characterize the dose-response, the proportion of ACR20 response at Week 12 will also be presented for each treatment group, along with the difference in ACR20 response proportion between evobrutinib and placebo, and the 95% CI for the difference. Details will be provided in the SAP.

The dose response will also be assessed via a modeling approach as additional supportive analyses. Details will be provided in the SAP.

Additional sensitivity analyses will be performed to assess the robustness of the primary missing data imputation method and will be described in detail in the SAP.

## **8.5.3 Analysis of Secondary Endpoints**

### **8.5.3.1 Key Secondary Efficacy Endpoints**

Analyses of all key secondary efficacy endpoints will be performed using the same approach as the ACR20, based on the mITT analysis set.

### **8.5.3.2 Key Secondary Safety Endpoints**

Analysis of safety secondary endpoints is described in Section [8.5.4.1](#).

### **8.5.3.3 Imaging Data and Other Efficacy Endpoints**

Analysis of the change from Baseline scores of the MRI data will be performed on the appropriate analysis sets (MRI analysis set for the RAMRIS and CARLOS scores) using a Mixed Model for Repeated Measures, with treatment arm as factors, and randomization strata, and Baseline as

covariates. Missing data will be handled as MAR. Other imputation methods will be provided in the SAP as additional sensitivity analyses.

Analyses of all other efficacy endpoints will be exploratory in nature and details will be further provided in the SAP.

### **8.5.3.4 Patient-reported Health Related Quality of Life (HRQoL)**

Change in SF-36 Physical Component Summary and Mental Component Summary scores (and their components) over time and change in FACIT-Fatigue score over time will be summarized using descriptive statistics.

Further details will be presented in the SAP that will be finalized before database lock.

## **8.5.4 Analysis of Safety and Other Endpoints**

### **8.5.4.1 Safety**

Analyses of safety will be carried out as follows.

Adverse events will be summarized by treatment group, severity, and relationship to IMP. Serious AEs, AEs leading to treatment discontinuation (permanent, temporary), and AEs leading to study withdrawal will be summarized by treatment group.

Adverse events will be coded according to the Medical Dictionary for Regulatory Activities (MedDRA). The number and percentage of subjects experiencing 1 or more treatment-emergent AEs (TEAEs) will be summarized according to the MedDRA system organ classes and preferred terms by treatment group, relationship to IMP, and severity. The severity of AEs will be graded using NCI-CTCAE v4.03 toxicity grades ([US Department of Health and Human Services 2010](#)).

Summary and analysis of AEs will be performed based on the 3-tier approach ([Crowe 2009](#)) as further detailed in the trial SAP.

Summary statistics will be used to present observed values and changes from Baseline in continuous laboratory parameters and vital signs. Shift tables will be used to present changes in categorical laboratory parameters. Figures may be generated to assist safety evaluation.

The 12-lead ECG data (RR [ms], PR [ms], QRS [ms], QT [ms], and QTcF [ms]) will be summarized for observed values and change from baseline values by treatment using descriptive statistics. Electrocardiogram outlier values will be summarized by treatment in frequency tables using number and percentage of subjects. Investigator reported overall interpretation results will be listed and tabulated by treatment using the number and percentage of subjects for each interpretation category (Normal, Abnormal Not Clinically Significant, Abnormal Clinically Significant, and Abnormal Overall). A concentration-QT analysis may be conducted.

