### 4.2 Key Secondary Objective

The key secondary objectives are:

- To further evaluate the efficacy and dose response of 12 weeks of treatment with evobrutinib in MTX-IR subjects with RA on stable MTX therapy by assessment of the signs and symptoms of RA, as measured by DAS28-hsCRP low disease activity (DAS28 < 3.2) rate at Week 12
- To further evaluate the efficacy of 12 weeks of treatment with evobrutinib compared to placebo in MTX-IR subjects with RA on stable MTX therapy by assessment of the signs and symptoms of RA, as measured by DAS28-hsCRP remission (DAS28 < 2.6) rate at Week 12
- To further evaluate the efficacy and dose response of 12 weeks of treatment with evobrutinib in MTX-IR subjects with RA on stable MTX therapy by assessment of the signs and symptoms of RA, as measured by ACR50 and ACR70 at Week 12
- To evaluate the safety of evobrutinib in MTX-IR subjects with RA on stable MTX therapy.

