#### 15.1.1.1 3-Tier Approach

The 3-tier approach is a systematic way to summarize and analyze adverse events (AEs) in clinical trials (Crowe 2009). AEs in different tiers are analyzed using different levels of statistical analyses.

Tier 1 AEs are provided in Appendix 18.10. Other AEs will be classified into Tier 2 or Tier 3 based on the Rule-of-3. If there are 3 or more subjects with the reported term in any treatment group, that term will be included in Tier 2. Otherwise, it will be included in Tier 3.

The Tier 1 and Tier 2 AEs will be assessed with the number and percentage of subjects having at least one occurrence, as well as the difference with placebo and corresponding 95% CI for between-group comparison. For the difference in crude rates, the CIs will be based on MN method (Miettinen 1985). No multiplicity adjustment will be applied.

The tier 3 AEs will be assessed via summary statistics and risk differences.

For each comparison of evobrutinib group with placebo, forest trees for Tier 1 and Tier 2 AEs will be provided as well, displaying the incidence rate and associated 2-sided 95% CI of difference.

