**Specific rules for SOC/PT tabulation**

All AEs recorded during the trial (ie assessed from signature of informed consent until the end of the Follow-up/End of Trial visit) will be coded according to the MedDRA and assigned to a SOC and PT.

SOC terms will be sorted alphabetically. The combined dose of evobrutinib (25 mg QD, 75 mg QD and 50 mg BID) will be computed and displayed in the table. PTs within each SOC will be sorted by descending frequency of this combined dose of evobrutinib, and then alphabetically if multiple PTs have the same frequency.

If a subject experiences more than one occurrence of the same TEAE during the trial, the subject will be counted only once for that treatment (the worst severity and the worst relationship to trial treatment will be tabulated).

In case a subject had events with missing and non-missing grades, the maximum of the non-missing grades will be displayed.

Exposure adjusted incidence rates (EAIR) are calculated as number of subjects with TEAE divided by the sum of the individual times of all subjects in the safety population from start of treatment to first onset of TEAE or end of treatment period, whichever occurs first. The incidence rate multiplied with 1000 would give the number of TEAEs expected in 1000 subjects within 1 year. EAIR of TEAEs will be presented by SOC and PT.

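### The adverse-event plan gives intervals for each evobrutinib dose against placebo but none for evobrutinib overall, and its tier rule counts cases arm by arm

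*Protocol*

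**What the plan says.** - **Objective.** Protocol 4.2 lists as a key secondary objective: "To evaluate the safety of evobrutinib in MTX-IR subjects with RA on stable MTX therapy". It names the drug and no particular dose.
- **Method.** Protocol 8.5.4.1 says: "Summary and analysis of AEs will be performed based on the 3-tier approach". It contains no interval method or tier threshold. The working rules are in the SAP.
- **Tiers.** SAP 15.1.1.1 takes Tier 1 from a list fixed in advance ("Tier 1 AEs are provided in Appendix 18.10"). Other terms are sorted by count: "If there are 3 or more subjects with the reported term in any treatment group, that term will be included in Tier 2". The remainder go to Tier 3. The treatment groups in SAP Table 4 are placebo and the three regimens, so the combined group is not one of them.
- **Output.** Tier 1 and Tier 2 terms get counts and percentages, "as well as the difference with placebo and corresponding 95% CI for between-group comparison". On method: "For the difference in crude rates, the CIs will be based on MN method". Forest plots are planned for each evobrutinib group against placebo, and no multiplicity adjustment is made. For the rest: "The tier 3 AEs will be assessed via summary statistics and risk differences".
- **Combined column.** The SOC/PT tabulation rules in SAP 15.1.1.3 add: "The combined dose of evobrutinib (25 mg QD, 75 mg QD and 50 mg BID) will be computed and displayed in the table". Preferred terms are sorted by it. No difference or interval against placebo is attached to it.

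**The concern.** The estimate closest to the stated objective, any evobrutinib against placebo, is shown as a frequency with no measure of precision, although its numerator and denominator are already to be programmed. Each planned interval uses one third of the exposed subjects.

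The tier rule has the same feature. A term outside Tier 1 with 2+2+2 evobrutinib cases and none on placebo (6/270 vs 0/90) gets no interval, while a term with three placebo cases and none on evobrutinib gets one. With three active arms and one control, counting within arms separates terms by how their cases are spread as well as by how many there are.

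Protocol 3.4 bases its important potential risks on nonclinical data and on compounds of a similar pharmacological class. Such effects could occur at every dose, and then the combined estimate is informative. At stake is how tightly a reader can bound an overall excess.

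**Working it through.** **Inputs.** 80 evaluable per group, about 11% loss, about 90 enrolled per group, 1:1:1:1 allocation (Protocol 8.1 and 8.2). Check: 80/(1 − 0.11) = 89.9, so 90. I assume all 90 per arm are treated, which gives 270 on evobrutinib and 90 on placebo. The plan states no precision or power figure for adverse events. All event rates below are assumptions.

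**Width at equal rates (normal approximation).** The ratio of combined to by-dose width is √[(1/90 + 1/270)/(1/90 + 1/90)] = √(0.01481/0.02222) = 0.816, so about 18% narrower. At a 5% rate the half-width is 196 × √(0.05 × 0.95 × 2/90) = 6.4 points by dose and 196 × √(0.05 × 0.95 × (1/90 + 1/270)) = 5.2 points combined.

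**MN intervals.** The limits are the values δ that solve (r₁ − r₀ − δ)²/V = 3.84, where V = [R₁(1 − R₁)/n₁ + R₀(1 − R₀)/n₀] × N/(N − 1) and R₁, R₀ are the maximum-likelihood rates under R₁ − R₀ = δ. Results in percentage points:

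| By dose | 95% CI | Combined | 95% CI | Narrower by |
|---|---|---|---|---|
| 9/90 vs 9/90 | −9.3 to 9.3 | 27/270 vs 9/90 | −8.5 to 6.3 | 20% |
| 7/90 vs 2/90 | −1.0 to 13.3 | 21/270 vs 2/90 | −0.4 to 9.9 | 28% |
| 8/90 vs 2/90 | −0.05 to 14.7 | 24/270 vs 2/90 | 0.7 to 11.2 | 29% |
| 5/90 vs 0/90 | 1.3 to 12.4 | 15/270 vs 0/90 | 1.4 to 9.0 | 31% |
| 2/90 vs 0/90 | −1.9 to 7.8 | 6/270 vs 0/90 | −1.9 to 4.8 | 31% |

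**Tier 3 terms.** With no placebo case, the most that can stay in Tier 3 is 2+2+2. Its combined interval (last row) includes zero. With 0/90 on placebo, 11/270 gives −0.07 to 7.2 and 12/270 gives 0.3 to 7.6, so 12 cases are needed to exclude zero.

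**How often terms stay in Tier 3.** If the true rate is p in each evobrutinib arm and 0 on placebo, P(Tier 3) = P(Bin(90, p) ≤ 2)³. This is 82% at 1%, 61% at 1.5%, 39% at 2%, 12% at 3% and 0.5% at 5%. The chance of Tier 3 together with at least three evobrutinib cases in total is 33%, 38%, 30% and 11% at 1%, 1.5%, 2% and 3%. The gap therefore concerns events at roughly 1% to 3%.

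**Chance that an interval excludes zero on the upper side** (exact enumeration, shared placebo arm):

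| Placebo vs every dose | One given dose | At least one of three doses | Combined |
|---|---|---|---|
| 2% vs 8% | 44% | 70% | 54% |
| 5% vs 13% | 48% | 73% | 58% |
| 10% vs 20% | 47% | 72% | 60% |
| 5% vs 5% (no effect) | 2.1% | 4.9% | 1.4% |

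If the risk sits at one dose only (2%, 2% and 8% vs 2%), the combined interval excludes zero 7% of the time, against 44% for that dose alone.

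**The case against.** **The by-dose display suits the design.** The trial is meant to inform the choice of a dose for Phase III, daily doses run from 25 mg to 100 mg, and the protocol synopsis calls safety descriptive. This stands: the by-dose rows should stay, and pooling dilutes a risk confined to one dose.

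**A reader might infer that the plan misses differences a combined analysis would find.** The figures do not support that. All three by-dose intervals are shown without adjustment, and the chance that at least one excludes zero (70-73%) is above the combined chance (54-60%). The combined row is better only than a single by-dose interval; against all three it offers one statement with fewer false flags.

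**A reader might also infer that events are compared only by dose, or that thinly spread events get no comparison.** That is too strong. Combined frequencies are displayed, Tier 1 terms get an interval whatever their count, and Tier 3 terms get risk differences. Nor can it be said that the class risks in Protocol 3.4 lack intervals: they may be in Tier 1, and the Tier 1 list is not visible in the documents available.

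**Three placebo cases entering Tier 2** follows from a rule that treats all arms alike. Taken by itself, it is not a fault.

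**Conclusion.** The point holds as a modest gap. The SAP specifies no interval for evobrutinib overall against placebo, and it sorts terms outside Tier 1 by single-arm counts. A combined row would be about 18-20% narrower at equal rates and about 30% narrower with few placebo events. For sparse terms it gives a tighter upper bound: 4.8 points at 6/270, against 7.8 at 2/90, with 0/90 on placebo. With no effect and a 5% rate in all arms, it falsely flags an excess in about 1.4% of cases, against 4.9% when three unadjusted intervals are read together.

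It would not raise the chance that some interval excludes zero, and it would not show an excess for any term now in Tier 3 with no placebo cases. The figures assume 90 treated per arm and, except where stated, equal risk at all doses. With 80 per arm, P(Tier 3) rises from 82% to 87% at a 1% rate and from 39% to 48% at 2%. The importance is low and nothing planned is invalid.

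**What to change.** In SAP 15.1.1.1:

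1. Add a combined-evobrutinib versus placebo row (risk difference with MN 95% interval) to the Tier 1 and Tier 2 tables and forest plots, beside the three by-dose rows.
2. Apply the Rule-of-3 to the combined evobrutinib count as well as to each treatment group.
3. State that the by-dose rows remain the display for dose-related effects and that the combined row is descriptive, like the rest of the safety analysis.

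The cost is SAP wording and one more row per term, using counts already planned for the SOC/PT tables. It needs no new data and does not touch the efficacy analysis or its error control. More terms enter Tier 2: under the rates assumed above, about 30-38% of terms with a true rate of 1-2% in each evobrutinib arm and 0 on placebo would move up. How many terms that means cannot be known in advance.
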